Study Design. This double-blind, randomized pilot clinical trial will prescreen an estimated 250 potential subjects, consent and further evaluate approximately 100 potential subjects, and ultimately enroll 70 subjects to ensure 40 subjects will provide a primary marijuana reduction outcome measure at four weeks post quit date. Subjects will be stratified by sex then randomized to one of two treatment groups (n=20 per drug group, 50% female): progesterone (PRO; 200mg 2x/day) or Placebo (PBO). They will take the medication for 5 weeks and will attend weekly clinic visits (see Visit Sequence & Procedure below for more information).

Setting: This project will be conducted at the Delaware Clinical Research Unit (DCRU). The DCRU has both inpatient and outpatient resources for the spectrum of biomedical research including special capabilities that were developed for study of substance use disorders. The Clinical and Translational Sciences Institute (CTSI), runs the DCRU and functions parallel to and supports the activities of the NIH funded CTSI, which it predicated. The DCRU includes: reception area, examination rooms, meeting rooms, clinical interview rooms, testing rooms for computer based performance tasks, a wet lab for handling bloods and other specimens, freezers (to -80°C), all essential staff offices, each with multiple telephone and computer lines through the University of Minnesota servers, locked limited access protocol, equipment and medication rooms, as well as secure cabinets for study files and essential supply and support areas and services.

Recruitment: To meet recruitment goals, we aim to enroll a total of 70 subjects (~6 subjects/month) to ensure a final sample size of 20 females and 20 males completing the study. Our primary recruitment method will be advertising in the mainstream media. While this type of recruitment can be challenging, our team has been successful with this form of recruitment. For example, our current study (PRO for smoking cessation) has had success with Facebook, Craigslist, TV, and radio advertising. Specifically, over the past seven months, we have received an estimated 300 phone calls from interested participants which resulted in the enrollment of 30 subjects (~8 subjects/month).

Study Sample. This study will enroll males (n=35) and females (n=35) who self-report use marijuana ≥4 days per week and are interested in changing their marijuana use. Specific eligibility criteria are as follows:

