Baseline Visit (Visit 3): Female subjects will be instructed to come into the clinic within three days of the start of their Luteal Phase for their baseline visit and to start medication (PRO or PBO). Female subjects will self-report menstrual cycle length at their screening visit and staff will determine when their Luteal Phase will most likely begin. Male subjects will be instructed to come into the clinic according to their assigned delay (per randomization list generated by the Statistical Analysis Core). This visit will occur seven days prior to quit date. At this visit, subjects will be randomized to PRO or PBO within strata defined by sex. The Statistical Analysis Core (SAC) will generate the randomization tables (one for each sex, 1:1 allocation using randomly permuted blocks of size 2 and 4), and the Clinical Trials Research Pharmacy will use it to determine randomization assignment. Randomization assignment will be stored in a secure file in a secure location at the Clinical Trials Research Pharmacy, to be shared only with the SAC. All other project staff including PI and study coordinator, as well as the participant, will remain blinded to the randomization assignment. At the baseline visit subjects will provide a blood sample (for hormone assessment), urine sample for THC, breath sample (to confirm smoking status via carbon monoxide breathalyzer), have their vital signs (blood pressure, heart rate, weight) measured, be informed of their quit date, and receive brief behavioral counseling to prepare for their quit date. At the end of this visit subjects will be compensated for their time, given study medication along with instructions for taking the medication (beginning at 8PM that day), as well as a clinic visit schedule for the remaining clinic visits. This visit will take approximately one hour to complete.

Marijuana Change Date Assignment: Change date (Week 0) will be set for 7 days following the Baseline Visit. Since this entails a delay of variable duration from Screening Visit 2 to Baseline Visit (thus impacting timing of medication initiation) across female subjects, each male subject will be matched to a female subject for a similar delay so that, across the male and female groups, study procedures will follow a similar chronology.

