Therefore, subjects will receive approximately \$340 (\$25 Screening Visits x 2 visits + \$20 follow-up visits x 7 visits + \$80 in bonus payments + an average of \$70 in BART payments).

Study Medication

Subjects will be stratified by sex and then randomly assigned to PRO or PBO, as described above. All medication (active and placebo) will be prepared by the University of Minnesota Clinical Trials Research Pharmacy, which is a specialized facility that prepares medication for clinical trials including our ongoing research. The research pharmacist ([name] Pharm D) will provide medications. There will be oversight and monitoring with regular audits by local regulatory boards including the IRB and DSMB. This study requires double-blind procedures, therefore progesterone will be over encapsulated and be identical to the placebo capsules. Medications will be discontinued at the Week 4 clinic visit. Adverse events will be assessed at each clinic visit.

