| MN Impulsive Disorders Interview: Buying, stealing, hair pulling, anger, gambling, sex, binge eating | MIDI | | | | | | | | |

| | | | | | | | | | |
|---|---------|---------|---------|---------|---------|---------|---------|---------|---------|
| Randomization: Progesterone or Placebo | | | RAND | | | | | | |
| Cannabis Use Disorder Identification Test: Disorder | CUDIT-R | | | | | | | | |
| Severity of Dependence Scale-Cannabis: Dependence | SDS-C | | | | | | | | SDS-C |
| Cannabis Withdrawal Scale: Withdrawal | CWS | | CWS |
| Marijuana Craving Questionnaire: Craving | MCQ-SF | | MCQ-SF |
| Reasons for Quitting Questionnaire: Marijuana | RFQ | | RFQ | | | RFQ | | RFQ | |
| Self-Efficacy Questionnaire: Confidence to resist marijuana | SE | | SE | | | SE | | SE | |
| Fagerström Test for Nicotine Dependence: Nicotine dependence | FTND | | | | | | | | |
| Minnesota Nicotine Withdrawal Scale: Withdrawal, craving | MNWS | | MNWS |
| Questionnaire for Smoking Urges: Intention to smoke, anticipation of relief from negative affect | QSU | | QSU |
| Cigarette Smoking Stage of Change Questionnaire: Readiness to quit smoking cigarettes | SOC | | SOC | | | SOC | | SOC | SOC |
| Columbia-Suicide Severity Rating Scale: Suicidal ideation | C-SSRS | | C-SSRS |
| Adverse Events: Since you last visit... | | | AE |
| Perceived Stress Scale: Perceived stress | | PSS |
| Profile of Mood States: Positive mood, arousal, vigor, elation, friendly, fatigue, tension-anxiety, depression-dejection, etc. | | POMS | POMS | POMS | | | | POMS | |
| Beck Depression Inventory-II: Depressive symptoms | | BDI-II |
| Adverse Childhood Experiences: childhood maltreatment | | ACE | | | | | | | |
| Life Event Occurrence Survey: Significant life events | | LEOS-R | | | | | | | LEOS-R |
| Leisure Time Exercise Questionnaire: Strenuous, moderate and mild exercise | | LTEQ |
| Behavioral Inhibition/Activation scales: Motivational systems (appetitive & avoidance) | | BIS/BAS |
| Barratt Impulsiveness Scale: Impulsivity and self-control | | BIS |
| Brief Self Control Scale: Ability to control problematic behaviors | | BSCS |
| Delay Discounting Task: Evaluates discount rates for rewards, impulsivity | | DD | | | | | | DD | |
| Debriefing Questionnaire: Perception of rand. assignment (PRO/PBO) | | | | | | | | DQ | |
| Study Satisfaction Survey: Taking meds, working with staff, etc. | | | | | | | | | SS |
| Time-Line Follow-Backs: | | | | | | | | | |

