Although uncomfortable, marijuana withdrawal symptoms do not pose significant health risks. Subjects who participate in this study will be asked to quit or reduce their marijuana use on an assigned quit date. This may result in increased irritability, anxiety, tension, decreased appetite or sleeplessness.

Adverse Events: An adverse event is any unwanted experience or event occurring during the course of a clinical trial. At each visit, research assistants will collect pertinent information on any AE's and meet with the Nurse Practitioner (NP) at least once per week. The NP will decide if the AE was related to the study medication and give recommendations for follow-up. In cases where the NP is unavailable or if the AE needs immediate attention, it will be escalated to the PI immediately for acknowledgment and recommendations.

The study investigators will follow all AEs to the point of a satisfactory resolution. A study subject may be withdrawn from the study if the PI determines it is the best decision for protection of the safety of the subject. All AEs will be assessed to determine if they meet criteria for an SAE. AEs will be quantified separately by sex and treatment groups and compared across treatment groups with Fisher's exact test (for binary events) or with chi-square test (for counts of events or event rates). The event will be documented as to whether there is 1) no relationship between the study drug and the adverse event, 2) the adverse event is unlikely related to administration of the study drug, 3) the adverse event is possibly related to study drug administration, or 4) the adverse event is probably related to the administration of the study drug.

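### The chi-square test planned for adverse event counts and rates appears to treat repeated events in one participant as independent, and so rejects too often if counts vary more than Poisson

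*Combined protocol and SAP*

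**What the plan says.** The only text on the AE analysis is in the Adverse Events paragraph of Trial Safety. It states that "AEs will be quantified separately by sex and treatment groups", and that they will be "compared across treatment groups with Fisher's exact test (for binary events") or "with chi-square test (for counts of events or event rates").

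The Study Medication section says "Adverse events will be assessed at each clinic visit", and the AE row of Table 1 carries the prompt "Adverse Events: Since you last visit". Table 1 schedules that row at Baseline and at Weeks 0 to 5. The Baseline Visit text has the first dose taken that evening, which leaves up to six assessments per participant after dosing.

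The documents do not state the unit of the chi-square test, a counting rule for an AE that continues across visits, a method for correlation within a participant, a significance level for AE tests, or an expected AE rate or spread.

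**The concern.** Binary data have their own test in the same sentence, so the chi-square test for counts or rates is most naturally read as a comparison of event totals per arm. That comparison is valid only if the variance of the total equals its mean.

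Several features of this trial make extra spread plausible:

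- Each participant is asked about AEs repeatedly.
- The plan calls sedation the most common effect of a medication taken daily for five weeks, so one person could report it at several visits.
- The withdrawal symptoms that the plan lists (irritability, anxiety, tension, appetite loss, poor sleep) are likely to occur together in the same person.
- Follow-up will differ between people. The plan will "ultimately enroll 70 subjects to ensure 40 subjects will provide a primary marijuana reduction outcome measure at four weeks post quit date", and those who leave after randomization, short of the final follow-up visit, are not replaced.

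At stake is the between-arm comparison of AE counts and rates. A small p-value there could be taken for a treatment effect when it reflects a few frequent reporters or the counting convention.

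**Working it through.** **No figure to reproduce.** The plan gives no level, AE rate or dispersion. The 5% two-sided level and the dispersion values below are assumptions.

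**Inputs from the documents.** "This study will enroll males (n=35) and females (n=35"), with "1:1 allocation using randomly permuted blocks of size 2 and 4" in each sex. This gives 70/2 = 35 per arm, or 17 to 18 per arm within sex. For the 40 expected with a Week 4 outcome it gives 20 per arm, or 10 per arm within sex.

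**Formula.** Let each participant's count have mean μ and variance Vμ, with n per arm and equal exposure. Call the arm totals A and B.

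1. The 1-df chi-square statistic on totals is (A−B)²/(A+B), compared with 3.84.
2. Under no treatment effect, Var(A−B) = 2nVμ and E(A+B) = 2nμ. The statistic therefore behaves like V times a chi-square variable on 1 df.
3. The rejection rate is 2[1 − Φ(1.96/√V)]. Neither n nor μ appears in it.

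The formula was checked by simulating 40,000 null trials per setting. Means were 0.5, 1, 2 or 4 AEs per person. Counts were Poisson, or negative binomial with shape k, for which V = 1 + μ/k.

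| V | 1.96/√V | Formula | Simulated, 20 or 35 per arm | Simulated, 10 per arm |
|---|---|---|---|---|
| 1 (Poisson) | 1.960 | 5.0% | 4.9–5.1% | 4.4–5.3% |
| 1.25 | 1.753 | 8.0% | 7.9–8.0% | 7.1% |
| 1.5 | 1.600 | 11.0% | 10.4–11.0% | 9.7–11.0% |
| 2 | 1.386 | 16.6% | 16.3–16.9% | 15.0–16.5% |
| 3 | 1.132 | 25.8% | 25.2–25.8% | 25.1–25.8% |

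**Effect of the missing counting rule.** Suppose distinct AEs are exactly Poisson with mean μ, but each is recorded at m visits. The count has mean mμ and variance m²μ, so V = m. Simulation with 20 or 35 per arm gave 16.4–17.4% for m = 2 and 25.7–26.9% for m = 3. Re-counting alone is therefore enough to inflate the test, without any AE-prone participants.

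**Participant-level alternatives on simulated null data.**

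- Fisher exact test on participants with at least one event, by exact enumeration at true rates of 10% to 50%: 1.2–2.8% with 20 or 35 per arm. It is conservative and does not depend on V.
- t test on per-person counts: 4.2–5.1% with 20 or 35 per arm, and 3.5–5.0% with 10.
- Wilcoxon test on per-person counts (3,000 trials per setting): 4.2–5.9% with 20 or 35 per arm, and 3.6–4.8% with 10.
- Quasi-Poisson (chi-square divided by the estimated dispersion, F reference): 4.6–6.0% with 20 or 35 per arm, and 4.6–7.5% with 10.

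**The case against.** **The unit is undefined, so the text may be incomplete and not wrong.** The wording does not exclude a chi-square test on participants classed by number of events. In simulation, with classes 0, 1 and 2 or more, that test kept its size at 4.7–5.0%. This stands as a possible reading. However, it fits poorly with event rates and is nowhere stated, so the sentence needs repair either way.

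**Re-counting is not established.** The investigators follow each AE to resolution and ask about the interval since the last visit. Both fit a log in which a continuing AE appears once. This also stands, so re-counting is a risk that the plan leaves open and not something it prescribes. Counting once would not remove clustering of different AEs within a person.

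**A sound test is already planned.** A reader might infer that the trial's whole safety comparison is unreliable, or that the chi-square test is the only between-arm safety test. The documents do not support either inference, because the same sentence plans the Fisher test for binary events.

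**One or two frequent reporters may not be enough.** With 20 per arm and a mean of 2, each arm expects 40 events. Significance then needs 20 extra events in one arm: 20²/100 = 4.0 exceeds 3.84, while 19²/99 = 3.65 does not. With 10 per arm and a mean of 1, it needs 11 extra (11²/31 = 3.90). So one or two people could create a signal from a balanced start only with very high counts. It would be easier for sparse single AE types or when the arms already differ by chance.

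**The p-values drive no decision.** The Analysis Plan describes an estimation pilot. The monitoring board receives blinded data by default, and analyses are run at study end. No text ties AE p-values to stopping or to the case for a larger trial. This stands and limits the impact.

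**Conclusion.** The point holds as a conditional defect of modest impact. On its natural reading, the chi-square test on AE counts or rates ignores repeated events within participants. It is too liberal to the extent that per-person counts exceed Poisson variation: about 8% to 26% at a nominal 5% for variance/mean ratios from 1.25 to 3, and 5% if counts are Poisson with no re-counting. More participants would not cure it.

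This rests on three assumptions: the test is applied to event totals, the level is two-sided 5%, and V lies in the range shown. A reader might go further and conclude that the test will give false signals far more often than 5%. The documents cannot show this, because they give no dispersion. A correction is still worthwhile, since the plan names a method that is valid only in the most favourable case and a better one needs no new data.

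**What to change.** Revise the AE analysis sentence to say three things.

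1. **Main comparison.** Report participants with at least one event, by AE type, arm and sex, using the Fisher exact test already planned.
2. **Counting rule.** Count an AE that continues across visits once.
3. **Counts and rates.** Replace the chi-square test with an analysis that uses one count per participant. The preferred choice is a permutation test of per-person counts or rates within sex, which follows the stratified randomization. The alternative is negative binomial or quasi-Poisson regression on the pooled sample, with sex as a factor and log follow-up time as offset.

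Within sex, with about 10 per arm, quasi-Poisson ran up to about 7.5% in the simulation, so the permutation test is preferable there.

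The change takes a few lines of text and no new data. It can be made at any time before the end-of-study analysis. The one statistical cost is wider uncertainty for count comparisons when counts are over-dispersed.

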- **Cigarette Smoking Stage of Change Questionnaire** (SOC; Prochaska et al, 1993) This 3-item questionnaire will be used to assess readiness to quit smoking cigarettes. It will classify the sample into two groups - those who are 1) in the "active/preparation" stage of quitting and those who are in the 2) "contemplation/pre-contemplation" stage.
- **Profile of Mood States** (POMS; McNair et al, 1971): On this 72-item form subjects use a 5-point Likert-type scale, to indicate 10 subscales (Evans et al 1998) including positive mood, arousal, vigor, elation, friendly, fatigue, tension-anxiety, depression-dejection, confusion, and anger-hostility. This item will only be completed once during the screening process. This item will be completed at Screening Visit 1. This item will be completed at each clinic visit thereafter.
- **Beck Depression Inventory-II** (BDI-II, Beck et al, 1996): This is the most commonly used screening measure for adults and will be used to assess depressive symptoms. This item will only be completed once during the screening process. This item will be completed at Screening Visit 1. This item will be

completed at each clinic visit thereafter.

- **Perceived Stress Scale** (PSS; Roberti et al, 2006): This ten item questionnaire will measure perceived stress. The items are rated on a 5-point scale, ranging from 0 (never) to 4 (very often), and they focus on events during the last week. The scale has adequate reliability and validity. This item will only be completed once during the screening process. This item will be completed at Screening Visit 1. This item will be completed at each clinic visit thereafter.
- **Columbia-Suicide Severity Rating Scale**: This questionnaire (C-SSRS; Posner et al, 2009) will be completed at each clinic visit to assess suicidal ideation, given this is listed as an SAE on the Prometrium label. If any item of suicidality is endorsed referrals to the appropriate mental health care will be made.
- **Sociodemographic Variables**: At the first screening visit we will collect information on age, race/ethnicity, education, income and other related variables. This item will be completed at Screening Visit 1 only.

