The Admin Core Director ([name]) and the Statistical Analysis Core Director ([name]) of the P50 will jointly organize review by the Data Safety and Monitoring Board (DSMB). The Project PI ([name]) will administratively oversee complying with reporting requirements. The DSMB will meet annually and will, post meeting, provide a summary of discussion, which will be conveyed to NIDA. This report will include subject demographics, expected versus actual recruitment rates, summary of any quality assurance or regulatory issues, summary of adverse events (AEs) or serious adverse events (SAEs) which may have occurred, and any changes in the protocol as a result of these issues. The DSMB will receive current data and blinded data unless a specific request or cause to view un-blinded data is evident. The final report will be complete and inclusive with the unblended data set.

The Project Coordinator ([name]) and PI ([name]) will meet on a weekly basis to review the study's progress. The team will meet regularly and as needed regarding data and project safety. Additionally, all key personnel will meet regularly regarding overall progress, specific problems and problem resolution. The daily monitoring of subjects will be the coordinator's responsibility.

Participants will be closely monitored throughout the trial. A summary of all data, with the exception of information that entails breaking the blind, will be provided to the DSMB at annual meetings. SAE's will be reported to the head of the DSMB when they have been identified and characterized. The chair of the DSMB may request a special meeting of the panel as needed. The Board will consist of Drs. [name] (Chair), [name], [name], and an expert in marijuana abuse (TBN). These individuals will serve to monitor all the SCOR projects involving human subjects, including this project.

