Serious Adverse Events (SAE): A serious adverse event is defined as an outcome that is 1) fatal or life-threatening, 2) significantly or permanently disabling or incapacitating, 3) requires or prolongs inpatient hospitalization, or 4) results in a congenital anomaly. SAE's, whether or not related to study medication, will be reported to the IRB and NIDA. All drug related adverse events of a non-serious nature are reported to the University of Minnesota's IRB on an annual basis. Serious adverse events will be reported by telephone to the IRB, and to NIDA and the FDA within the three days of our receipt of information regarding the event and written reports will be submitted within ten days. If a subject either withdraws from the study or the investigator decides to discontinue a subject due to SAE, the subject will have appropriate follow-up medical monitoring. Monitoring will continue until the problem requiring hospitalization was resolved or stabilized with no further change expected, is clearly unrelated to study medication, or results in death. Outcome of SAEs will be periodically reported to NIDA. A summary of the SAEs that occurred during the previous year will be included in the annual progress report to NIDA. Finally, the PI will ensure that serious adverse events are reported to NIDA via the serious adverse event tracking and reporting system at <https://saetr.snia.nih.gov/>.

The Principal Investigator will then take appropriate action (including study modification) as agreed upon by these monitoring groups including the DSMB when needed. The Principal Investigator will determine whether the seriousness of the event warrants removal of the participant from the study. Appropriate diagnostic and therapeutic interventions will be initiated and the participant will be medically followed and kept under observation as long as medically indicated. After the review of the data, the DSMB report will make recommendations about whether the trial should continue with or without modifications, or be terminated. Any potential conflict of interest in the Data and Safety Monitoring Board will be disclosed.

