Protection against Risk. Subjects will be told the potential risks involved in this study. Although risks to subjects in the proposed study are minimal, the following actions will be taken to minimize these risks. We will exclude subjects with health conditions that may be exacerbated by their participation. Subjects will be monitored regularly by medical personnel employed by the study. [name] (PI) will be available for emergency phone calls 24 hours/day and for office visits in case of problems. Blood will be collected by trained phlebotomists to reduce the risks involved with blood draws.

During Progesterone administration, the first dose of the study medication will be taken at 8 PM to minimize possible sedation from initiation of progesterone treatment. Subjects will be warned about using caution when driving a motor vehicle or operating machinery. Subjects will also be warned about the side effects associated with Progesterone. Further, although unlikely, the study physician ([name], PI) will be alert to the earliest

manifestations of thrombotic disorders including thrombophlebitis, cerebrovascular disorders, pulmonary embolism, and retinal thrombosis (PDR, 2002). If any of these occur or are suspected, the study medication will be discontinued immediately and medical treatment will be sought.

Potential Benefits of the Proposed Research to the Subjects and Others

Whereas no assurance can be made to an individual subject that he/she will personally benefit from such research, the experience should be beneficial. Subjects will have the opportunity to learn about their marijuana use behavior and receive behavioral counseling. Society may benefit from a better understanding of the role of sex hormones on marijuana use and impulsivity. A better understanding of this relationship will help improve treatment strategies for marijuana use. The risks in relation to the potential benefits are minimal to the individual research subject and virtually nonexistent to society in general.

Trial Efficacy

No interim analyses of efficacy are planned for the proposed study.

References

Adamson, S. J., & Sellman, J. D. (2003). A prototype screening instrument for cannabis use disorder: the Cannabis Use Disorders Identification Test (CUDIT) in an alcohol-dependent clinical sample. *Drug and Alcohol Review*, 22(3), 309–315. [PMID: 15385225]

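### The four-outcome SAE definition does not capture suicidal ideation, which the plan says the label lists as an SAE, or uncomplicated outpatient thrombotic events, so both can miss expedited reporting

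*Combined protocol and SAP*

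**What the plan says.** The section on Serious Adverse Events (SAE) opens: "A serious adverse event is defined as an outcome that is 1) fatal or life-threatening, 2) significantly or permanently disabling or incapacitating". The list ends: "3) requires or prolongs inpatient hospitalization, or 4) results in a congenital anomaly". The Adverse Events section says every adverse event is checked against the SAE criteria, and the available text gives no others.

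SAEs, whether or not related to study medication, are telephoned to the IRB, NIDA and FDA within three days, with written reports within ten. For the rest: "All drug related adverse events of a non-serious nature are reported to the University", once a year. Under the Data Safety and Monitoring Plan, SAEs also go to the head of the DSMB once identified and characterized. Other events reach the board in the summary for its annual meeting.

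Three other places bear on what counts as serious:

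- **C-SSRS (study measures).** The scale "will be completed at each clinic visit to assess suicidal ideation, given this is listed as an SAE on the Prometrium label". The stated response is: "If any item of suicidality is endorsed referrals to the appropriate mental health care will be made".
- **Potential Risks and Benefits (Trial Safety).** After describing stroke, coronary disease, venous thromboembolism and breast cancer reported with long-term combined hormone treatment, the text calls these serious adverse events. It excludes people with a history of thrombotic and related conditions as a precaution.
- **Protection against Risk.** The study physician watches for early "manifestations of thrombotic disorders including thrombophlebitis, cerebrovascular disorders, pulmonary embolism, and retinal thrombosis". Medication stops if one occurs or is suspected. No reporting step is given.

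**The concern.** The plan uses two notions of seriousness. The measures section justifies a scale at every visit by the SAE status of suicidal ideation on the label. The SAE section then defines seriousness by a closed list of outcomes that ideation on its own does not meet. Thrombotic events raise the same question, less strongly.

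The classification matters because every prompt report to an outside body depends on it. It also decides whether relatedness acts as a filter: SAEs are reported regardless of cause, whereas the annual IRB report takes only drug-related events. At stake is whether the IRB, NIDA, FDA and DSMB hear of such an event while enrolment is still running.

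**Working it through.** The plan gives no figure to reproduce. The check follows two events through the written rules and then sets the reporting interval against the length of the trial.

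**Step 1: apply the four outcomes.**

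| Outcome | Ideation on the C-SSRS, no admission | Uncomplicated thrombophlebitis, outpatient |
|---|---|---|
| Fatal or life-threatening | no | no |
| Disabling or incapacitating | no | no |
| Inpatient hospitalization | no | no |
| Congenital anomaly | no | no |

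Neither event is an SAE as the definition is written.

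**Step 2: follow the reporting routes.**

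| Recipient | SAE | Not an SAE, judged drug related | Not an SAE, judged unrelated |
|---|---|---|---|
| IRB | 3 days by telephone, 10 days in writing | annual report | no route stated |
| NIDA | 3 days, 10 days | annual DSMB summary only | annual DSMB summary only |
| FDA | 3 days, 10 days | no route stated | no route stated |
| DSMB head | event-driven, no number of days given | annual meeting | annual meeting |

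Inside the study team, an event needing immediate attention goes to the PI at once in all three columns.

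**Step 3: compare the interval with the trial.** Inputs: 70 participants at about 6 per month (Recruitment), five weeks of medication (Study Design) and annual DSMB meetings.

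- Enrolment: 70 / 6 = 11.7 months, against up to 12 months between meetings.
- Dosing: 35 / 30.4 = 1.15 months per person.
- Share finished dosing if the first meeting falls *t* months after the first dose, with steady enrolment and all 70 dosed: 6 × (*t* − 1.15) / 70, and zero before 1.15 months.
- *t* = 1: 0%.
- *t* = 6: 6 × 4.85 / 70 = 42%.
- *t* = 12: 6 × 10.85 / 70 = 65.1 / 70 = 93%.
- Average if *t* is equally likely anywhere from 0 to 12: (6 / 70) × 10.85² / (2 × 12) = 42%.

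The plan does not give the DSMB calendar, so the result is a range of 0% to 93%.

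**The case against.** The strongest reply is that these events are neither missed nor left unmanaged. Adverse events are collected at every visit, any endorsed suicidality item leads to referral, urgent events go to the PI at once, the coordinator and PI meet weekly, and the DSMB chair may call a special meeting. All of that stands, so it would be wrong to infer that participants go without care. But none of these steps prompts a report to an outside body, and a chair who has not been told of an event has no reason to call a meeting.

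Four stronger readings are tempting and are not supported:

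- *The plan classifies all thrombotic events as serious.* It does not. Protection against Risk sets a rule for stopping medication, which is not a seriousness classification, and calls these events unlikely. The risk text's reference to serious adverse events concerns estradiol with a synthetic progestin, and it adds that natural progesterone is not known to cause thromboembolism. Pulmonary embolism, stroke or retinal thrombosis would often meet one of the four outcomes anyway. What remains is mainly the uncomplicated outpatient case, so the thrombotic part is secondary.
- *Such events always reach the IRB once a year.* This holds only for those judged drug related. For others no IRB route is stated.
- *Nearly everyone would have finished dosing before the board could react.* That assumes a first meeting about twelve months after the first dose. The board oversees all projects of the parent programme, so its calendar need not start with this trial.
- *The DSMB cannot see data by arm.* It "will receive current data and blinded data unless a specific request or cause to view un-blinded data is evident", so access for cause is allowed. How the board sees routine tables is a separate matter.

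**Conclusion.** The inconsistency is real and internal to the document. For suicidal ideation it is direct: the plan cites the label's SAE listing as its reason for measuring ideation, then applies a definition that ideation alone cannot meet. For uncomplicated outpatient thrombotic events it is weaker but of the same kind.

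The gap lies in classification and external reporting. The consequence is a wait of up to about 12 months instead of three days for the IRB, or no stated route if the event is judged unrelated. Prompt notice to NIDA, the FDA and the DSMB is lost as well. One annual cycle is about as long as the 11.7 months of planned enrolment, so a full wait could span most of the trial.

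This rests on reading the four outcomes as a closed list, on the stated enrolment rate, and on the available text. A stretch between the DSMB description and the data-handling text was not available to check. Events that lead to admission, threaten life or disable are already covered. The point should be corrected but does not call the trial's validity into question.

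**What to change.** Reconcile the SAE section with the C-SSRS entry, the risk text and Protection against Risk:

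1. Add an important-medical-event criterion, or a named list of events of special interest. It should cover suicidality on the C-SSRS, at a threshold the study physician sets in advance, and suspected thrombotic events.
2. Put these events on the existing three-day route to the IRB, NIDA and FDA, whatever their judged relation to study medication.
3. State a time for notice to the DSMB chair, since the present text gives none even for SAEs.

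The cost is protocol wording and a few extra expedited reports. The change needs no new visit, test or data item, and the clinical handling already described stays as it is.
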